7.0 Risk/Benefit Analysis

7.1 Anticipated Risks Associated with the Study Device conjunction with a colonoscope

The Pure-Vu is used in conjunction with a colonoscope during a colonoscopy procedure. Hence, the complications associated with using the Pure-Vu are anticipated to be similar to those associated with the colonoscopy procedure. As with any colonoscopy procedure, when using the Pure-Vu there are some risks

Document Title: Randomized Controlled Study Comparing Colon Evaluation With The Pure-Vu System To A Standard Colonoscopy In Patients Who Are High Risk For Inadequate Bowel Preparation (“RESCue”)	Document No. CL00048	Version 1.0	Page 18 of 41
---	--------------------------------	-----------------------	---------------

of a missed lesion, bowel perforation, pain, or bleeding. Although the risks of the procedure with the Pure-Vu System are expected to be comparable to conventional colonoscopy (0.35%), the device is an add-on to a colonoscope.

The Pure-Vu system was tested in an animal study including 35 pigs and in preliminary clinical studies including 97 subjects. No major complication or serious adverse events occurred within the course of those studies.

In addition, clinical studies demonstrated an excellent cleansing effectiveness; the Pure-Vu System improved the cleansing level from 25% at baseline to 99% after the cleansing was operated and in 98% of the subjects the cecum were reached and the procedures completed successfully.

Considering the residual risks and the potential and the risk against benefit assessment, it can be concluded that the system may offer potential benefit to the subjects along with no significant risk increase.

7.2 Residual Risks Associated with the Study Device

The Pure-Vu System is an FDA 510(k) cleared device which is indicated to cleanse poorly prepped colons during colonoscopy.

Residual risk is defined as the risk remaining after controls have been implemented. Risks associated with the use of the Pure-Vu System were mitigated in accordance to the EN ISO 14971:2012 risk management process. For more details please request the risk analysis report.

7.3 Potential Benefits to the Subject

The potential benefits of the Pure-Vu System are the cleaning technology that may improve visualization, reduced reliance on subject pre-procedure colon preparation and reduced need for repeated colonoscopies required due to insufficient colon preparation, these consequently may reduce pain, discomfort, risks, costs and lost productivity.

Considering the residual risks and the risk against benefit assessment, it can be concluded that the system may offer potential benefit to the subjects along with no significant risk increase compared to the standard of care procedure.

Document Title: Randomized Controlled Study Comparing Colon Evaluation With The Pure-Vu System To A Standard Colonoscopy In Patients Who Are High Risk For Inadequate Bowel Preparation (“RESCue”)	Document No. CL00048	Version 1.0	Page 19 of 41
---	--------------------------------	-----------------------	---------------

8.0 Study Objectives

8.1 Primary Objective

To evaluate the frequency of bowel cleansing adequacy after Pure-Vu as compared to standard colonoscopy (“Control”) in subjects who are high risk for inadequate colon preparation

8.2 Secondary objectives

1. Assess the willingness of consented subjects to pay for Pure-Vu prior to colonoscopy
2. Colonoscopy procedural measures for Intervention and Control arms
3. Endoscopists’ experience
4. Safety assessment for all subjects on the day of procedure per endoscopist
5. Post-colonoscopy patient experience and safety check with scripted phone call 1-3 days after colonoscopy
6. Assess the willingness of consented subjects to pay for the Pure-Vu System 1-3 days after colonoscopy

9.0 Study Endpoints

9.1 Primary Endpoint

A comparison between the two study arms (i.e., Pure-Vu vs. standard colonoscopy) of the rate of overall cleansing as well as cleansing per segment will be evaluated by the BBPS scoring index (Bowel preparation adequacy defined as BBPS ≥ 2 in each segment)

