3.0 Protocol Synopsis

Study Summary	
Study Purpose	The aim of this study is to assess the efficacy of Pure-Vu in the outpatient colonoscopy setting.
Objective	The objective of this study is to evaluate the bowel cleansing after Pure-Vu use in outpatient subjects at high risk for inadequate colon preparation.
Study procedures	
• Eligible subjects will be consented• Subject will be randomized and undergo procedure either in the Control arm (standard of care) or with the Pure-Vu System
Protocol Number	CL00048
Protocol Title	Randomized Controlled Study Comparing Colon Evaluation With the Pure-Vu System To A Standard Colonoscopy In Patients Who Are High Risk For Inadequate Bowel Preparation (“RESCue”)
Study Sponsor	Motus GI Medical Technologies, [name]
Study Type	Multicenter, prospective, randomized controlled trial
Study Product	Pure-Vu System
Study Phase	Post-market
510 (k) Number	K191220 Class II
Study Location	United States
Study Duration	Study period will last approximately 12 months

Document Title: Randomized Controlled Study Comparing Colon Evaluation With The Pure-Vu System To A Standard Colonoscopy In Patients Who Are High Risk For Inadequate Bowel Preparation (“RESCue”)	Document No. CL00048	Version 1.0	Page 7 of 41
---	--------------------------------	-----------------------	--------------

Planned Follow-Up	Follow-up call will be conducted 1-3 days after the procedure
Subject Population	Eligible outpatient subjects who are indicated for colonoscopy procedure
Sample Size	88 subjects inclusive of a 10% attrition rate (44 per arm)
Planned # of Sites	Up to 4 clinical sites
Primary Endpoint	Boston Bowel Preparation Score (BBPS) after attempts to cleanse the colon are completed. (Bowel preparation adequacy defined as BBPS ≥ 2 in each segment)
Secondary Endpoints	
The following secondary endpoints will be determined:
 
1. Assess the willingness of consented subjects to pay for Pure-Vu prior to colonoscopy2. Colonoscopy procedural measures for Intervention and Control arms3. Endoscopists' experience4. Safety assessment for all subjects on the day of procedure per endoscopist5. Post-colonoscopy patient experience and safety check with scripted phone call 1-3 days after colonoscopy6. Assess the willingness of consented subjects to pay for the Pure-Vu System 1-3 days after colonoscopy

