9.2 Secondary Endpoints

1. Assess the willingness of consented subjects to pay for Pure-Vu prior to colonoscopy
 - a. Would want Pure-Vu bowel cleansing device to be used on day of colonoscopy if preparation were inadequate (“Yes” or “no”)
2. Colonoscopy procedural measures for Intervention and Control arms
 - a. Duration: Insertion and withdrawal time without intervention other than cleansing

Document Title: Randomized Controlled Study Comparing Colon Evaluation With The Pure-Vu System To A Standard Colonoscopy In Patients Who Are High Risk For Inadequate Bowel Preparation (“RESCue”)	Document No. CL00048	Version 1.0	Page 20 of 41
---	--------------------------------	-----------------------	---------------

- b. Colonoscopy completion: “Yes” or “no;” if “no” then record most proximal extent of exam and reason exam was incomplete (it is acceptable to switch to a different scope if needed due to anatomical reasons)
- c. Polyp detection - For each polyp: Location, size, morphology (pedunculated, sessile, flat), removal technique (cold biopsy, hot biopsy, cold snare, hot snare, EMR), histology
- d. Non-polyp colonoscopy findings: Finding, location
- e. Assessment of need for early repeat colonoscopy (defined as endoscopist recommendation for early repeat colonoscopy due to preparation): “Yes” or “no”

3. Endoscopist experience

- a. Intervention arm
 - i. Ease of use of Pure-Vu (visual analogue scale 0-10)
 - ii. Efficacy of Pure-Vu (visual analogue scale 0-10)
- b. Intervention and Control arms
 - i. Technical difficulty performing colonoscopy (visual analogue scale 0-10)

4. Safety assessment for all subjects on the day of colonoscopy by endoscopist

- a. Type, incidence, severity, Relation to procedure and clinical consequence(s) of adverse event.

5. Post-colonoscopy patient experience with scripted phone call 1-3 days after colonoscopy

[figure not shown]
- a. Patient satisfaction
 - i. Colonoscopy experience overall (analogue scale 0-10)

6. Assess the willingness of consented subjects to pay for Pure-Vu 1-3 days after colonoscopy

[figure not shown]
- a. Would want Pure-Vu bowel cleansing device to be used in the future for colonoscopy if preparation were inadequate (“Yes” or “no”)

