13.0 Statistical Analysis

13.1 Sample Size Determination

Assuming 60% preparation adequacy in the Control arm, and 90% preparation adequacy in the Intervention arm, a total sample size of 80 participants (40 per arm) has 85% power (using 2-sided alpha 0.05). To account for an expected dropout rate of 10% per arm, 44 participants per arm will be enrolled, for a total of 88 patients.

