13.3 Primary Endpoint Analysis

The primary statistical hypothesis is that the cleansing level post cleansing with the Pure-Vu (Intervention arm) will be significantly improved as compared to the cleansing level post standard colonoscopy procedure (Control arm). The Intervention (Pure-Vu) and Control (standard colonoscopy) arms will be compared with respect to preparation adequacy (BBPS ≥ 2 in every segment). In case of incomplete procedure, the segments that are not evaluated due to dirtiness are assigned a score of 0. In case of non-evaluated segment due to anatomical challenges (stricture, mass, etc.) segments will be excluded from analysis.

The risk ratio was estimated along with a 95% confidence interval, and use the Mantel-Haenszel test with stratification by site to test whether preparation adequacy differs between the two arms (with a 2-sided alpha 0.05). All main analyses will follow the intent-to-treat principle. In case of substantial deviations from the protocol, secondary per-protocol analyses will also be carried out.

Document Title: Randomized Controlled Study Comparing Colon Evaluation With The Pure-Vu System To A Standard Colonoscopy In Patients Who Are High Risk For Inadequate Bowel Preparation (“RESCue”)	Document No. CL00048	Version 1.0	Page 27 of 41
---	--------------------------------	-----------------------	---------------

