13.4 Secondary Endpoints Analysis

Secondary dichotomous outcomes (intubation, adverse events) will be analyzed similarly using the Mantel-Haenszel test, with site as stratification variable (with a 2-sided alpha 0.05). Secondary continuous outcomes (timing, number of polyps, patient and endoscopist satisfaction) will be analyzed using linear regression, with site as a covariate.

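### Does listing per-segment cleansing under the primary endpoint in section 9.1 leave the trial with more than one primary test?

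*Combined protocol and SAP*

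**What the plan says.** Section 9.1 of the combined protocol and SAP describes the primary endpoint as a between-arm comparison in which "the rate of overall cleansing as well as cleansing per segment will be evaluated by the BBPS scoring index". A parenthesis there defines adequacy as a score of at least 2 in each segment.

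The other places that bear on the primary question are these:

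- Section 8.1 gives one objective: "To evaluate the frequency of bowel cleansing adequacy after Pure-Vu as compared to standard colonoscopy".
- The synopsis (section 3.0) names the "Boston Bowel Preparation Score (BBPS) after attempts to cleanse the colon are completed" and repeats the each-segment definition. It lists no separate segment comparison.
- Section 13.1 sizes the trial on one pair of rates: "Assuming 60% preparation adequacy in the Control arm, and 90% preparation adequacy in the Intervention arm".
- Section 13.3 opens with one hypothesis, "The primary statistical hypothesis is that the cleansing level post cleansing with the Pure-Vu (Intervention arm) will be significantly improved". It then says that the arms "will be compared with respect to preparation adequacy (BBPS ≥ 2 in every segment". One site-stratified Mantel-Haenszel test at two-sided 0.05 follows. Its only segment-level rules concern segments that could not be evaluated: those too dirty to assess score 0, and those missed for anatomical reasons are left out.
- Section 9.2 lists "Colonoscopy procedural measures for Intervention and Control arms" and other items, but not segment cleansing.
- Section 13.4 reads "Secondary dichotomous outcomes (intubation, adverse events) will be analyzed similarly using the Mantel-Haenszel test", again without segments.

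**The concern.** Section 9.1 joins two comparisons under one heading, and only the first is carried into the analysis section. A comparison that stands under the primary endpoint but has no test, alpha share, testing order or declared status is the usual way for an unplanned multiplicity problem to enter a trial. There are three segments (section 6.3), so a literal reader could count four primary comparisons, each at 0.05.

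The stake would be the claim made at the end. If overall adequacy missed significance but one segment favoured Pure-Vu, 9.1 taken alone could be cited to present that segment as a primary result, and no sentence expressly forbids it.

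**Working it through.** **1. What the plan commits to.** Take the elements of a confirmatory test in turn and ask which quantity each belongs to.

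| Element | Where | Overall adequacy | Each segment |
|---|---|---|---|
| Objective | 8.1 | yes | no |
| Named under primary endpoint | 9.1 | yes | yes |
| Assumed rates and power | 13.1 | yes | no |
| Hypothesis, test, alpha | 13.3 | yes | no |
| Secondary listing or test | 9.2, 13.4 | not applicable | no |

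Sections 8.1 and 13.1 say only adequacy. The each-segment meaning comes from the definition in the synopsis, 9.1 and 13.3. With that definition, every element of the primary test belongs to overall adequacy.

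**2. The plan's power figure.** Inputs from 13.1: 40 evaluable per arm, 0.60 against 0.90, two-sided 0.05. With b(·) the binomial probability,

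power = Σᵢ Σⱼ b(i; 40, 0.60) · b(j; 40, 0.90) · 1[Fisher p ≤ 0.05] = 0.852.

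This reproduces the stated 85%. In a single stratum, the Mantel-Haenszel test gives 83.9% with continuity correction and 90.1% without.

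**3. Would 85% fit a plan with four primary comparisons?**

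- Any one suffices, Bonferroni split: alpha = 0.05/4 = 0.0125. Power for the overall test falls to 66.9% (Fisher) or 73.9% (pooled normal). Restoring 85% needs 51 per arm (pooled) before dropout.
- All four must succeed: about 14% to 70% (uncorrected Mantel-Haenszel), assuming equal segment rates and a latent correlation of 0 to 0.9.

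Neither matches 13.1. This check cannot exclude a third reading, four tests at an unsplit 0.05, because that leaves the overall test's power at 85%. Section 13.3 excludes it as a planned analysis by specifying one test.

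**4. Size if segments were misused.** Assumptions: 40,000 null trials per scenario; 40 per arm in 4 equal sites; three segments from a latent normal model with correlation 0.3, 0.6, 0.8 or 0.9; segment rates solved so that overall adequacy is 60% in both arms. The test statistic over sites k is

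z = |Σₖ(aₖ − Eₖ)| / √(Σₖ Vₖ), with 0.5 taken off the numerator in the corrected form,

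where aₖ, Eₖ and Vₖ are the observed count, hypergeometric mean and hypergeometric variance. Section 13.3 does not say which form applies, so both are shown. The table gives the percentage of null trials in which a segment is significant in favour of Pure-Vu while overall adequacy is not.

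| Scenario | Form | 0.3 | 0.6 | 0.8 | 0.9 |
|---|---|---|---|---|---|
| Equal segments (82/78/73/70% adequate) | uncorrected | 5.6 | 5.1 | 4.4 | 3.4 |
| | corrected | 2.7 | 2.7 | 2.5 | 1.9 |
| Right segment 10 points lower | uncorrected | 5.8 | 4.9 | 4.2 | 3.5 |
| | corrected | 2.4 | 2.3 | 2.3 | 2.0 |

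The planned overall test rejects in 5.1 to 5.4% of null trials uncorrected and 2.9 to 3.1% corrected. Its part favouring Pure-Vu is 2.6 to 2.8% and 1.4 to 1.6%. Adding the ends of the ranges gives the total favourable error under misuse:

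- uncorrected: 2.6 + 3.4 = 6.0% to 2.8 + 5.8 = 8.6%
- corrected: 1.4 + 1.9 = 3.3% to 1.6 + 2.7 = 4.3%

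The nominal one-direction rate is 0.05/2 = 2.5%. Other assumed segment rates, including the pre-cleansing 60/62/47% from the inpatient study in section 6.3, move the segment-only figure to 3.5 to 6.4% uncorrected and 1.7 to 3.8% corrected. Monte Carlo error is about 0.1 point.

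**The case for a change.** The best case for a change is that 13.3 settles the matter only by implication. It never mentions the segment comparisons that 9.1 promises, so it does not demote them. Its segment rules deal with unevaluated segments and are not a segment analysis. The each-segment parenthesis defines adequacy and leaves the separately named comparison without a status. Segment results will probably be reported, since section 6.3 does so for the inpatient study. Under misuse the favourable error could more than double, and one sentence would remove the doubt.

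The textual part stands: the status is unstated, and 9.1 does speak of a comparison between arms. The consequence does not follow. The bowel preparation scale is scored by segment, so reporting segments beside the composite built from them is ordinary description. No section says that one significant segment meets the primary claim. The inflation needs two steps that the plan never takes: testing each segment at 0.05, and calling the result primary after the overall test has failed. Anyone reviewing such a claim would hold it against 13.1 and 13.3 and find one powered, specified test.

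Moving the segments into the secondary analysis would not clearly help. Section 13.4 tests dichotomous secondary outcomes by Mantel-Haenszel at 0.05, so segments placed there would be tested by default unless exempted.

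**Conclusion.** The concern does not call for a change. The trial has one primary test: overall adequacy, compared by a site-stratified Mantel-Haenszel test at two-sided 0.05. Followed as written, that test gives a sound primary result, and N = 88, alpha and the 85% power are untouched.

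What is left is a missing detail about component comparisons. Analysts would fill it sensibly by reporting adequacy per segment descriptively, for example as a risk ratio with a 95% interval, with no confirmatory weight. The misuse figures (segment-only favourable error of 3.4 to 5.8% uncorrected, 1.9 to 2.7% corrected, in the two main scenarios) are conditional on a use that the plan does not contain. They also rest on segment rates and correlations that the documents do not give.

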9.2 Secondary Endpoints

1. Assess the willingness of consented subjects to pay for Pure-Vu prior to colonoscopy
 - a. Would want Pure-Vu bowel cleansing device to be used on day of colonoscopy if preparation were inadequate (“Yes” or “no”)
2. Colonoscopy procedural measures for Intervention and Control arms
 - a. Duration: Insertion and withdrawal time without intervention other than cleansing

Document Title: Randomized Controlled Study Comparing Colon Evaluation With The Pure-Vu System To A Standard Colonoscopy In Patients Who Are High Risk For Inadequate Bowel Preparation (“RESCue”)	Document No. CL00048	Version 1.0	Page 20 of 41
---	--------------------------------	-----------------------	---------------

- b. Colonoscopy completion: “Yes” or “no;” if “no” then record most proximal extent of exam and reason exam was incomplete (it is acceptable to switch to a different scope if needed due to anatomical reasons)
- c. Polyp detection - For each polyp: Location, size, morphology (pedunculated, sessile, flat), removal technique (cold biopsy, hot biopsy, cold snare, hot snare, EMR), histology
- d. Non-polyp colonoscopy findings: Finding, location
- e. Assessment of need for early repeat colonoscopy (defined as endoscopist recommendation for early repeat colonoscopy due to preparation): “Yes” or “no”

3. Endoscopist experience

- a. Intervention arm
 - i. Ease of use of Pure-Vu (visual analogue scale 0-10)
 - ii. Efficacy of Pure-Vu (visual analogue scale 0-10)
- b. Intervention and Control arms
 - i. Technical difficulty performing colonoscopy (visual analogue scale 0-10)

4. Safety assessment for all subjects on the day of colonoscopy by endoscopist

- a. Type, incidence, severity, Relation to procedure and clinical consequence(s) of adverse event.

5. Post-colonoscopy patient experience with scripted phone call 1-3 days after colonoscopy

[figure not shown]
- a. Patient satisfaction
 - i. Colonoscopy experience overall (analogue scale 0-10)

6. Assess the willingness of consented subjects to pay for Pure-Vu 1-3 days after colonoscopy

[figure not shown]
- a. Would want Pure-Vu bowel cleansing device to be used in the future for colonoscopy if preparation were inadequate (“Yes” or “no”)

10.0 Study Design

Study Flowchart

Document Title: Randomized Controlled Study Comparing Colon Evaluation With The Pure-Vu System To A Standard Colonoscopy In Patients Who Are High Risk For Inadequate Bowel Preparation (“RESCue”)	Document No. CL00048	Version 1.0	Page 21 of 41
---	--------------------------------	-----------------------	---------------

11.0 Selection and Enrollment

After providing informed consent, the subject will sign the sites' designated IRB approved informed consent form (ICF). Enrollment of up to 88 subjects is planned.

Subjects' participation in the study will last approximately 2 days, including the procedure day, and one follow up call during the follow up period (1-3 days after the procedure). Subjects will be considered for the study if they meet the specific inclusion and none of the exclusion criteria.

11.1 Inclusion/Exclusion Criteria

Inclusion Criteria

1. Adults > age 22
2. Elective outpatient colonoscopy by participating gastroenterologist
3. Stool clarity grade 1-3 at presentation for colonoscopy

Document Title: Randomized Controlled Study Comparing Colon Evaluation With The Pure-Vu System To A Standard Colonoscopy In Patients Who Are High Risk For Inadequate Bowel Preparation ("RESCue")	Document No. CL00048	Version 1.0	Page 22 of 41
---	--------------------------------	-----------------------	---------------

Exclusion Criteria

1. Not competent to consent
2. Bleeding disorder – known or suspected
3. Hereditary Gastrointestinal Cancer syndrome
4. Known PT INR > 1.5
5. Known elevated PTT
6. Anti-platelet agent or anticoagulant (other than aspirin or nonsteroidal agent) which has not been stopped for the colonoscopy
7. Known platelet count < 50,000
8. Known absolute neutrophil count < 1,000
9. History of surgical colon resection
10. Pre-colonoscopy intent to enter terminal ileum
11. Prior incomplete colonoscopy due to technical & non-bowel preparation related reasons
12. Regular use of non-topical steroid
13. Pregnant
14. Prisoner or institutionalized for any reason
15. Psychiatric illness greater than mild
16. Colonoscopy without anesthesia administered (MAC) sedation
17. Diverticulitis
18. Active inflammatory bowel disease (Crohn's, Ulcerative Colitis, or Indeterminate)
19. Known or suspected colon stricture

11.2 Withdrawal Criteria

Subjects may withdraw from the study at their own request or at the request of their legally acceptable representative. The investigator may withdraw a subject from the study at any time for the following reasons:

1. Severe side effects clearly related to the study device.
2. Presence or appearance of exclusion criteria.
3. Appearance of accompanying diseases rendering further participation in the study impossible.
4. A significant protocol violation, as determined either by the sponsor or the investigator
5. Subject noncompliant with study procedures

The sponsor must be informed in each withdrawal case. For screen failures, and those satisfying inclusion/exclusion criteria but choosing not to participate in this study, the following will be recorded:

Document Title: Randomized Controlled Study Comparing Colon Evaluation With The Pure-Vu System To A Standard Colonoscopy In Patients Who Are High Risk For Inadequate Bowel Preparation (“RESCue”)	Document No. CL00048	Version 1.0	Page 23 of 41
---	--------------------------------	-----------------------	---------------

Age, gender identity, indication for colonoscopy, stool clarity grade, reason for screen failure (if screen failure).

